### 3.1.3 Exploratory objectives.

Exploratory objectives are not part of primary or secondary outcomes and the exact analyses methods are not detailed here. To assess if water supplementation during one year leads to alterations in

- Reported diet intake. This objective is exploratory but reported diet intake regarding alterations in e.g. sugar sweetened beverages and adherence to Nordic Diet Recommendations 2023 can have an important mediating effect on both primary and secondary endpoints. Reported diet intake was collected using a software from the Swedish National Food Agency, and they declined continuation of the license from last quarter of 2023. Thus, we have missing data in subjects who had not completed their V8 before that time point. We estimate approximately 30% of missing data for the diet analyses (i.e. do not have complete data at baseline and V8). We plan exploratory analyses to test if water vs control therapy leads to differences in change of intake of main nutrients (protein, carbohydrates and fat energy intake relative to total caloric intake) over the 12-month period. These analyses will be performed using t-test (treatment group differences between delta values).

The first step of statistical analysis will be to produce descriptive statistics for some baseline parameters on reduced population (those with baseline and at least one post-baseline value), by intervention group and compare those results with the ITT population. Variables taken into account are those potentially impacting the primary outcome (fasting glycemia) and could be the sex (Male/Female), the age at enrolment (Years), the BMI at baseline ( $\text{kg}/\text{m}^2$ ), the total energy intake at baseline ( $\text{kcal}/\text{day}$ ) from three non-consecutive days of 24-h dietary recall, if possible, 2-h plasma glucose level from OGTT at baseline ( $\text{mmol}/\text{L}$ ) and the waist circumference (cm). If we notice a clinical imbalance between study groups (control and intervention groups in the reduced population vs. the ITT population) for those variables, they could be considered as potential covariates in sensitivity models for primary and secondary analysis. Three other variables could also be considered for the sensitivity analysis: newly diagnosed with T2DM (Yes/No), management of T2DM (initiation of intensive lifestyle therapy if possible and initiation of hypoglycemic drug therapy) and drug therapy impacting the fasting glycemia (Yes/No).

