The second step will be driven by both previous results (the real number of missing data and potentially imbalanced covariates detected in the previous step). The idea is to perform sensitivity analyses for primary and secondary endpoints with dietary records (minimum baseline and one post-baseline value; maximum 3 data points per subject) including covariates that tend to cause imbalance between the intervention study groups.

- Gut microbiome composition. This is a second exploratory objective. Currently, we have only saved stool samples in the biobank, but since we do not yet have funding for microbiome profiling, it is unclear which method will be used (level of resolution i.e. 16S vs metagenomic shotgun sequencing) will require completely different statistics and bioinformatics. Thus it is not possible at this stage to provide a statistical analysis plan for this potential exposure. If any impacts of water treatment on primary or secondary outcomes are observed, and if funding allows measurement, a SAP - adjusted to the method of choice - will be written at a later stage.
- Plasma metabolome: Also for this third exploratory objective, funding is not currently available and range methodological resolution and cost is wide. Thus, like described for the microbiome, if funding allows measurement, a SAP- adjusted to the method of choice - will be written at a later stage.

[figure not shown]

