## 5.6 Analysis of primary criteria

### 5.6.1 Description of primary outcome measure

The primary outcome measure is between group comparison of the change from baseline to 12-month of fasting plasma glucose.

Variable name	Variable source 	Type 	Unit	Set 
Change of fasting plasma glucose from baseline to 6-and 12-months	D	C	mmol/L	ITT, PP

2. *(R)aw or (D)erived data*
4. *(C)ontinuous or (O)rdinal or (N)ominal*
5. *Intention to treat (ITT) or Per Protocol (PP)*

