### 5.6.2 Analysis of primary outcome parameters

The primary analysis (intention-to-treat) will compare the between study groups (intervention vs control treatment) LS-means differences on the changes from baseline to 12 months and from baseline to 6 months in fasting plasma glucose. The main analysis will be based on a linear mixed model with fasting plasma glucose change from baseline to study visits where it is measured during the study (6 and 12 months) as dependent variable. This model produces unbiased estimates under the assumption that missing data are missing at random. The model will be adjusted (through fixed effects) for sex (because of the stratified randomization), baseline value of fasting plasma glucose, treatment, study visit and interaction between treatment and study visit. We will in the mixed regression analysis model within-patient correlation to decrease exponentially with number of days between measurements or through an AR(1) model. The choice of correlation structure specifies the variance-covariance matrix in the mixed regression model. The choice of covariance structure rests on principles of parsimony, simplicity and prior beliefs, rather than post-analysis testing. Model assumptions will be assessed through visual inspection of plots of suitable regression residuals. The estimated LS-mean differences between treatment levels for the change in fasting plasma glucose from baseline to 12 months and baseline to 6 months, the corresponding 95% confidence intervals (CIs) and p-values will be provided. The same analyses will be conducted on the imputed data set (see “Missing Data” sub-section under section 4.1) and the per protocol data set. The analyses will be conducted using SAS PROC MIXED.

Sensitivity analysis as described in Section 4.1, part “Missing Data” could be performed. Conclusions regarding the inclusion of baseline characteristics in the linear mixed model will be based on clinical significances.

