### 5.7.2 Analysis of secondary outcome parameters

New-onset diabetes is defined as 2 consecutive fasting plasma glucose values  $\geq 7.0$  mmol/L or 2-hour post OGTT value of  $\geq 11.0$  mmol/L after the baseline exam (V3). In addition, new onset diabetes is considered present if diagnosed by a physician outside of the current study, as assessed in the questionnaire (answering yes on having had a physician diagnosis of diabetes or having been prescribed

medication for diabetes) after the baseline exam (V3). All individuals with a diagnosis of diabetes at or before the baseline exam (V3) will be excluded in the analysis of incidence of diabetes.

The difference in diabetes incidence between the intervention and control group will be analyzed using logistic regression with diabetes incidence as the binary outcome and treatment arm as exposure variable and reported as the odds ratio (OR) including 95 % CI for diabetes incidence in intervention vs control. As the randomization should lead to no difference in diabetes risk factors, the main analysis will only be adjusted for sex (as the randomization is stratified by sex, this covariate will be included in all outcome analyses), but we will also add a sensitivity analysis to adjust for key diabetes risk factors at baseline (fasting glucose, diabetes status, BMI, age), if there is a clinically significant difference in these factors between treatment groups despite the randomization.

Cardiometabolic risk factors will be analyzed using the same method as for the primary outcome, but with baseline value for the actual factor as a covariate instead of baseline value of fasting plasma glucose.

In addition, to assess the possible association between change in fasting plasma glucose levels, copeptin, other cardiometabolic risk factors, other blood laboratory parameters and urine laboratory parameters, we propose to analyze correlation(s) between delta value of outcome parameters and delta value of the efficacy parameters (e.g. urine volume, urine osmolality and plasma copeptin) with Pearson or Spearman correlation analyses.

- Outcome parameters are fasting plasma glucose and all secondary continuous outcome parameters listed in section 5.7.1 above.

We emphasize that in these correlation analyses, copeptin will be regarded both as an outcome parameter and as an efficacy parameter.

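### SAP 3.1.3 lets the optional dietary-subset sensitivity models adjust for newly diagnosed diabetes and for starting diabetes therapy, which follow randomisation and depend on the outcome

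*SAP*

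**What the plan says.** SAP 3.1.3 proposes a two-step exploration in subjects with dietary records. The first step compares this reduced population with the ITT population on sex, age at enrolment, baseline BMI, baseline energy intake, baseline 2-hour glucose and waist circumference. If a clinically relevant imbalance appears, "they could be considered as potential covariates in sensitivity models for primary and secondary analysis". The section then adds: "Three other variables could also be considered for the sensitivity analysis: newly diagnosed with T2DM (Yes/No), management of T2DM", followed in brackets and after by "initiation of intensive lifestyle therapy if possible and initiation of hypoglycemic drug therapy) and drug therapy impacting the fasting glycemia (Yes/No". The second step runs the sensitivity models for primary and secondary endpoints, "including covariates that tend to cause imbalance between the intervention study groups".

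Four other places bear on this:

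- **SAP 5.6.1:** "The primary outcome measure is between group comparison of the change from baseline to 12-month of fasting plasma glucose".
- **SAP 5.6.2:** the main model contains sex, "baseline value of fasting plasma glucose, treatment, study visit and interaction between treatment and study visit". It has no covariate measured after baseline.
- **SAP 5.7.2:** "New-onset diabetes is defined as 2 consecutive fasting plasma glucose values" of at least 7.0 mmol/L, or a 2-hour OGTT value at or above a stated limit, after V3. A physician's diagnosis or prescribed diabetes medication after V3 also counts. Incidence is analysed by "logistic regression with diabetes incidence as the binary outcome and treatment arm as exposure variable".
- **SAP 4.1, Missing data:** adjustment is limited to the baseline value of the outcome, sex, and (as a sensitivity analysis) baseline age, BMI or diabetes status if the arms differ.

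**The concern.** The covariate list mixes two kinds of variable. Most entries are fixed before treatment starts. New diabetes and the start of therapy for it happen during follow-up and are consequences of high follow-up glucose. A model of glucose change that includes them no longer estimates the effect of being assigned to water. It compares arms among people with the same follow-up diabetes status, and so removes part of any real effect.

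The selection step adds to this. Imbalance between arms in a baseline variable is chance. Imbalance in new diabetes may be the treatment effect itself. If the imbalance criterion were applied to these variables, a working intervention would make their inclusion more likely.

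At stake is how the sensitivity result is read. An estimate that shrinks for this reason could be taken as evidence that the primary finding is fragile.

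**Working it through.** **1. Timing of each variable.**

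| Variable in SAP 3.1.3 | Timing on the wording | Link to the outcome |
|---|---|---|
| Newly diagnosed T2DM | Follow-up, on the natural reading; baseline diabetes status is covered separately in SAP 4.1 | Defined in 5.7.2 partly by follow-up fasting glucose; is a secondary outcome |
| Management of T2DM (initiation of therapy) | Follow-up | Triggered by high glucose |
| Drug therapy affecting fasting glycaemia | Not stated | A legitimate covariate if it means use at V3, which SAP 5.5 records |

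After baseline, fasting glucose is scheduled only at 6 and 12 months (protocol Table 1). On scheduled visits, the two-value criterion is therefore a thresholded function of the same two measurements that form the dependent variable in SAP 5.6.2.

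**2. Anchor on the plan's own figure.** SAP 3.3 gives a difference of 0.14 mmol/L, SD 0.58, 80% power and two-sided 0.05:

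n = 2 × (1.960 + 0.842)² × 0.58² / 0.14² = 269.4, so 270 per group.

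This reproduces the SAP. With 544 subjects split 46/54, power is 80.1%, and the standard error of the difference is 0.58 × √(1/250.2 + 1/293.8) = 0.050.

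**3. Size of the attenuation.** Regress 12-month change on arm and baseline glucose, with and without a new-diabetes indicator, in very large simulated samples. Attenuation = 1 − (estimate with indicator / estimate without).

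- From the documents: true effect −0.14, SD of change 0.58, threshold 7.0 mmol/L.
- Assumed, because the documents do not give them: baseline mean and SD (below), slope of change on baseline −0.3, residual correlation between 6 and 12 months 0.5, subjects with baseline glucose of 7.0 or more excluded.

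| Baseline mean / SD | Rule | Control incidence | Without | With | Attenuation |
|---|---|---|---|---|---|
| 5.6 / 0.5 | both visits ≥7.0 | 0.4% | −0.1401 | −0.1376 | 2% |
| 5.8 / 0.6 | both visits ≥7.0 | 1.1% | −0.1404 | −0.1349 | 4% |
| 6.1 / 0.7 | both visits ≥7.0 | 2.6% | −0.1414 | −0.1303 | 8% |
| 5.6 / 0.5 | either visit ≥7.0 | 2.9% | −0.1394 | −0.1279 | 8% |
| 5.8 / 0.6 | either visit ≥7.0 | 5.8% | −0.1399 | −0.1217 | 13% |
| 6.1 / 0.7 | either visit ≥7.0 | 11.2% | −0.1388 | −0.1096 | 21% |

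A second set, with baseline means 5.4, 5.7 and 6.0 and SD 0.6, gives about 1%, 3% and 7% when both values are required, and about 4%, 9% and 17% when the 12-month value alone decides. Across both sets the ranges are 1-8% and 4-21%.

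The largest shifts in the table are 0.1414 − 0.1303 = 0.011 and 0.1388 − 0.1096 = 0.029 mmol/L. These are 0.22 and 0.58 of the standard error of 0.050. The dietary subset is smaller, so its standard error would be larger and these fractions smaller.

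**4. Zero effect.** With a true effect of 0, the models with and without the indicator both return 0 to within simulation error. Attenuation needs an effect to attenuate.

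**5. Adding drug initiation.** Assume a 1.0 mmol/L fall in half of those with 6-month glucose of 7.0 or more. The effect without either covariate is −0.127 to −0.136. Adjusting for diabetes alone gives −0.109 to −0.135; adjusting for diabetes and drug gives −0.111 to −0.136.

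**6. Diabetes incidence as the outcome.** If the covariate equals the 5.7.2 definition, it predicts the outcome perfectly, the logistic model separates, and the odds ratio for water cannot be estimated. If it means only a physician's diagnosis after V3, every flagged subject is still a case by definition.

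**The case against.** The strongest reply is about reach. The text sits under exploratory objectives, uses permissive wording, and concerns only subjects with dietary records. A reader might infer that the primary result is biased. The documents do not support that: the main model in SAP 5.6.2 contains none of these variables, and the sensitivity analysis it refers to is the one in SAP 4.1, which uses baseline covariates. This part of the reply stands.

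On size, the reply also has force. The fasting criterion in SAP 5.7.2 needs two consecutive values, so few subjects would meet it within 12 months and the attenuation is then small. The OGTT and physician-diagnosis routes would add cases, but they were not simulated.

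Three further inferences go too far:

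- **That all three variables must go.** The third has no stated timing. Non-insulin-treated type 2 diabetes is eligible and baseline oral antidiabetic use is recorded, so baseline use would be a sound covariate.
- **That attenuation grows when drug initiation is also included.** The runs in step 5 do not show this; the two ranges are nearly the same.
- **That the SAP definitely plans to adjust diabetes incidence for itself.** SAP 5.7.2 gives that outcome its own baseline covariates, and 3.1.3 does not assign covariates by endpoint. It is a gap in wording that 3.1.3 leaves open.

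The reply does not remove the central point. As written, 3.1.3 permits these covariates in models for the primary and secondary endpoints. That falls outside the rule in SAP 4.1, and because inclusion is optional it can be decided after results are seen.

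**Conclusion.** The concern holds for the optional dietary-subset sensitivity models in SAP 3.1.3, and only there. Newly diagnosed diabetes and initiation of diabetes therapy are, on the natural reading, post-randomisation consequences of glucose and should not be covariates in a model for the effect of water on glucose.

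If water lowers fasting glucose by 0.14 mmol/L, adjusting for new diabetes would understate the effect by about 1-8% under the two-consecutive-values rule and about 4-21% if a single value suffices. These figures rest on the assumed baseline distribution, the incidence it implies, and the assumed slope and correlation. They also come from a 12-month regression rather than the full mixed model. The direction, toward zero, was the same in every setting with a true effect. The consequence is a sensitivity analysis that may mislead modestly. It is worth correcting because the error is clear and the correction is easy.

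**What to change.** In SAP 3.1.3:

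1. Remove newly diagnosed T2DM and management of T2DM (initiation of therapy) from the candidate covariates.
2. Define drug therapy affecting fasting glycaemia as use at baseline (V3).
3. State that every covariate, including waist circumference, is a value measured before treatment starts, and align the list with the rule in SAP 4.1.
4. If glucose-lowering therapy started during follow-up is of interest, specify a separate sensitivity analysis that treats it as an intercurrent event, with the estimand stated. One option is to set glucose after drug start to missing and impute it.

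Items 1 to 3 cost SAP wording only, with no new data and no change to the primary analysis. Item 4 adds one specified analysis and needs the start date of any such therapy.

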### 3.2 Study design

The study is a parallel-group RCT with two arms during 12 months. Subjects with the age of 20-75 years will be randomized to the water-intervention (1.5 L total on the top of habitual intake) and control group (1:1). The randomization will be stratified by gender to pursue equal distribution of intervention and control group for both male and female subjects. Both groups will receive general lifestyle advice (general oral and written advice on diet and physical activity). Reusable Bluetooth water bottles, which are volume sensitive and can be linked to an Android or iPhone application for individual monitoring purposes will be provided to subjects in the active treatment arm.

Study subjects will be recruited from 4 ongoing population studies in the Scania region encompassing altogether approximately 20 000 individuals within the current age span. Copeptin will be measured in -80 degrees frozen plasma samples from these 4 population studies. Individuals having a copeptin concentration of  $>6.1$  pmol/L (women) or  $>10.7$  pmol/L (men) will be invited to participate in the screening and inclusion process of this study. If fewer than expected will be recruited from these 4 studies, letters of invitation will be sent to inhabitants of the City of Malmö with surroundings, and inhabitants will also be invited through advertisements in local newspapers and social media. The same copeptin cut-off values will be used for inclusion to the study regardless of which invitation process that was used to include the participant.

All included individuals are low drinkers with high urine osmolality ( $U_{osm} \geq 600$ ) and low urine volume ( $U_{vol} \leq 1,5L$ ) as specified in the following figure.

Clinic visits are performed at 8 time points: visit 1, visit 2, baseline (visit 3, V3), 3 weeks and 3, 6 (visit 6, V6), 9 and 12 (visit 8, V8) months at which cardiometabolic risk factors and hydration parameters are measured (not all parameters at all time points). The study design is visualized in the Figure below.

### 3.3 Sample size

The primary outcome parameter is the difference between active (=extra water) and control treatment in the change of fasting plasma glucose between baseline and 12 months. We use prior effect estimates from the largest RCT for diabetes prevention study in Europe, i.e. the Finnish Diabetes Prevention Study (FDPS) (New Engl J Med 2001;344:1343-50), which compared individual life style counselling (active treatment) with general oral and written life-style advice (control treatment) in relation to risk of new onset type 2 diabetes and change of plasma glucose concentration and found a 58% decreased relative risk of diabetes. After 12 months, the fasting glucose in the active treatment group was reduced by  $4 \pm 12$  mg/dL vs a  $1 \pm 12$  mg/dL increase in the control group with the mean difference of 5 mg/dL of the 12-month change of fasting glucose being highly significant ( $P < 0.001$ ).

To obtain sufficient statistical power to detect a clinically significant effect size, we base the power calculation on an effect of water vs control that is at least 50% of what is considered an epoch changing effect of lifestyle i.e., the difference observed in the FDPS, while assuming the standard deviation for the change ( $s = 0.67$  mmol/L) as observed in FDPS. To be able to detect  $\geq 50\%$  of that effect (a difference of 2.5 mg/dL = 0.14 mmol/L between treatments in 12-month change) we need 319 evaluable subjects in both the active and control treatment group at a power of 80% and a 2-tailed significance level of =0.05, a total of 638 evaluable subjects. As the glucose measurement in the study used a more recent and exact method, the standard deviation of the change of glucose was recalculated by the DSMB in October 2022 from the first completed 357 study participants ( $s = 0.58$  mmol/L). With this smaller standard deviation, the power (with all other assumptions unchanged) was 270 evaluable subjects per group, i.e.  $n=540$  evaluable subjects in total. When also taking into account a dysbalance (with slightly higher drop-out rate in subjects in the intervention group), a total of 544 evaluable subjects were estimated to be needed for 80% power.

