control that is at least 50% of what is considered an epoch changing effect of life style, i.e. the difference observed in the FDPS, while assuming the standard deviation for the change ($s = 0.67$ mmol/L) as observed in FDPS. In order to be able to detect $\geq 50\%$ of that effect (a difference of $2.5 \text{ mg/dL} = 0.14 \text{ mmol/L}$ between treatments in 12-month change) we need 319 subjects in both the active and control treatment groups at a power of 80% and a 2-tailed significance level of < 0.05 . Experiences from the WIT (see above) indicate 8-10% lost to follow-up during 12 months. As our study subjects are “healthy subjects at risk” rather than patients, we anticipate a higher drop-out rate (up to 20%). Based on the power calculation ($n=319+319$) **we will enrol 400 individuals in each treatment group (n=400 in active and n=400 in control arm), i.e. a total number of 800 individuals**, to have a final sample size robust to lower compliance than anticipated. The power calculations and statistics of our study are performed by the chief statistician [name] at “Region Skåne Clinical Trials”.

Statistical Analysis Plan: (Responsible statistician: [name]): Please see separate file.

Ethical considerations: this study is conducted in compliance with the principles of the ‘World Medical Association Declaration of Helsinki’ (59th WMA General Assembly, Fortaleza, Brazil, October 2013), ICH guidelines for Good Clinical Practice as appropriate for nutritional products, and local legislation of the country in which the research is conducted, whichever affords the greater protection to the participants. Therefore, this study, as any study involving human subjects, will be registered in a publicly accessible database (ClinicalTrials.gov) before recruitment of the first subject.

This protocol and supportive documentation provided to the subjects, such as information and informed consent sheets and Forms, were submitted to the applicable Ethics Committee in Lund by [name] according to local regulations. Approval from the Ethics Committee was obtained on 15 Dec 2016. Ethics Committee meetings are planned every 6 weeks. An amendment will be submitted to the Ethics Committee in Lund in December 2017, prior to the commencement of any study activities.

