### 5.1.3 Populations

We expect a final study sample for intention to treat analysis of at least n=544 evaluable study subjects who have completed the protocol (i.e. with at least 2 fasting glucose measurements, meaning at V3 and at either V6 or V8 or at both V6 and V8). We expect a dysbalance in the final study sample (46% intervention vs 54% control therapy) due to dysbalance in the drop-out rate between intervention and control groups.

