## **7 Changes in the SAP with respect to the protocol**

SAP Section	Change	Rationale
3.3	Sample size	The reason for the recalculation is that the instruments used are more accurate in the measurements than the instruments used in the Finnish Diabetes Prevention Study (FDPS). The pooled standard deviation of delta fasting plasma glucose (mmol/L) at month 12 is 0.58.

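### The 319 per group (638) printed as 80% power gives about 75% on its stated inputs; 80% needs about 360 (720), as the SAP's own 270 at SD 0.58 also implies

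*SAP*

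**What the plan says.** Under its Sample size heading, the protocol states "we need 319 subjects in both the active and control treatment groups at a power of 80" per cent. It then allows for up to 20% drop-out and concludes that "we will enrol 400 individuals in each treatment group".

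SAP section 3.3 repeats the calculation and makes clear that the 319 are evaluable: "we need 319 evaluable subjects in both the active and control treatment group at a power of 80" per cent, at "a 2-tailed significance level of =0.05, a total of 638 evaluable subjects". The effect is "a difference of 2.5 mg/dL = 0.14 mmol/L between treatments in 12-month change", and the SD of the change is 0.67 mmol/L, taken from the Finnish diabetes prevention trial.

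The section goes on to report that the SD was recalculated in October 2022 from the first 357 completed participants as 0.58 mmol/L. On that basis, "the power (with all other assumptions unchanged) was 270 evaluable subjects per group", or 540 in total, raised to 544 for unequal drop-out. Section 7 logs the change and gives the SD as the only reason: "The pooled standard deviation of delta fasting plasma glucose (mmol/L) at month 12 is 0.58". Section 5.1.3 carries the new target forward: "We expect a final study sample for intention to treat analysis of at least n=544 evaluable study subjects", with an expected split of 46% to 54%.

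**The concern.** All inputs to the 319 are printed, so it should reproduce, and it does not. It also sits a few lines above a second figure, 270, that is said to differ from it only through the SD. For a comparison of two means, the required number is proportional to the square of the SD. The pair can therefore be tested against each other without choosing a formula, and it fails that test.

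What is at stake is the record of a sample size reduction made during the trial. Such a change is read closely, and its starting point should follow from the stated assumptions. A reader who finds that the smaller SD does not connect 319 to 270 may come to doubt the 544, which is correct. The protocol's 400 per arm was derived from the same 319, so its 80% claim has the same fault.

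**Working it through.** **Inputs.** Difference δ = 0.14 mmol/L, SD σ = 0.67 (later 0.58), two-sided α = 0.05 and power 80%, from SAP 3.3; 1:1 allocation from SAP 3.2. The protocol's Sample size paragraph uses the same δ, σ = 0.67, α and power.

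**Formula.** Number per group, normal approximation: n = 2(1.960 + 0.8416)²(σ/δ)² = 15.70 × (σ/δ)².

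**1. The plan's second figure (σ = 0.58).** n = 15.70 × (0.58/0.14)² = 269.4, so 270. This matches the SAP. With a 46:54 split the total is 540/(4 × 0.46 × 0.54) = 543.5, so 544. This also matches, with power 80.1% (80.0% by the t-test). The formula is evidently the one the SAP used.

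**2. The plan's first figure (σ = 0.67).** n = 15.70 × (0.67/0.14)² = 359.5, so 360 per group and 720 in total (361 per group by the t-test). The SAP prints 319 and 638.

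**3. Power at the printed size.** The standardised difference is 0.14/(0.67 × √(2/319)) = 2.639, and Φ(2.639 − 1.960) = 0.751 (0.750 by the t-test). At the 320 per group left from 400 after 20% drop-out, it is 0.753 (0.751 by the t-test).

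**4. The two figures against each other.** If only the SD changes:
- 270 × (0.67/0.58)² = 360.3
- 319 × (0.58/0.67)² = 239.1

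So 270 leads back to 360, and 319 leads down to 239.

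**5. Other readings that might give 319.**

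| Variant | n per group |
|---|---|
| Units of mg/dL (2.5 and 12) | 362 |
| Most favourable rounding of the printed values (0.145, 0.665) | 331 |
| Least favourable rounding (0.135, 0.675) | 393 |
| One-sided 5% | 284 |
| 90% power | 482 |
| 75% power | 318 |

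None of the readings at the stated 80% power reaches 319. For 319 to give 80% power, the SD would have to be 0.14 × √(319/2)/2.8016 = 0.631, or the difference about 0.149; neither is in the documents. Drop-out is not the explanation either: the SAP calls the 319 evaluable, and the allowance is added afterwards (319/0.8 = 398.75, hence 400). The 75% row comes close, but whether 319 arose that way is conjecture.

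**6. Size of the discrepancy.** 720/638 = 1.13, so 80% power needed 13% more evaluable subjects than printed. On a common basis the smaller SD lowers the requirement by (720 − 540)/720 = 25%; the printed figures show (638 − 540)/638 = 15%. With 20% drop-out, 360 evaluable would have meant enrolling 360/0.8 = 450 per arm. At the SD later observed (0.58), 319 per group would have had 86% power.

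**The case against.** The strongest reply is that 319 is history. It has been replaced by 544, the replacement is correct and logged, and the SAP already refers to data from September 2024, so the old figure can no longer steer enrolment or analysis. This stands, and it limits the point to a correction of the record. It does not make the sentence right: SAP 3.3 is current text, states the 319 in the present tense, and uses it as the base for the reduction.

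A second reply is that the published values are whole mg/dL. If the underlying difference and SD were rounded integers, the requirement could lie anywhere from about 275 to 485 per group; for example, a half-difference of 2.66 mg/dL with SD 12 gives about 319. But the plan prints 2.5 mg/dL, 0.14 and 0.67 mmol/L. At the plan's own conversion, 2.66 mg/dL is 2.66 × 0.67/12 = 0.149 mmol/L and would print as 0.15; an SD of 11.5 mg/dL would print as 0.64. Carrying 2.66 mg/dL to SD 0.58 also gives about 240 per group, not 270.

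A third reply is that the protocol also cites 8–10% loss from a related water trial. At that loss, 400 per arm leaves 360 to 368 evaluable and 79.9% to 80.8% power by the t-test. That is true of the enrolment figure and should be acknowledged. It does not rescue the stated claim, because the protocol attaches its 80% to 319 per group and plans for up to 20% loss.

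Finally, the primary model adjusts for baseline glucose and sex, which could raise power. To bring the SD from 0.67 to 0.631, covariates would have to explain 1 − (0.631/0.67)² = 11% of the variance. Neither document claims such a gain, and the 270 reproduces without one.

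Neither document states a percentage reduction, so the 25% and 15% above only describe the gap; they are not a further error.

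**Conclusion.** The figure is wrong as printed in both documents. With a difference of 0.14 mmol/L, SD 0.67 and a two-sided 5% test, 319 per group gives about 75% power, five points below the stated level, and 80% needs about 360 per group (720). It also contradicts the SAP's own 270 at SD 0.58. The 270, the 540 and the 544 are correct, and no current target, analysis or threshold depends on 319.

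These are unadjusted two-sample planning figures with equal groups, except for the 46:54 check of the 544. The documents give no correlation from which to quantify the gain from baseline adjustment. The correction should be made because it concerns the stated basis of a mid-trial sample size change, but it does not affect the validity of the result.

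**What to change.** In SAP 3.3:
- Keep 319/638 as the figure used in the protocol, and state that on its inputs (0.14 mmol/L, SD 0.67) it corresponds to about 75% power, and that 80% would have needed about 360 per group (720).
- Show the recalculation on one basis: 360/720 at SD 0.67, then 270/540 at SD 0.58, then 544 with the 46:54 split. Say plainly that 720 was never the trial's target.
- Reword the sentence that calls 270 a power, so that it gives 270 as the required number per group.

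Record the correction in the Section 7 row for 3.3. The protocol figure need not be replaced. If the protocol is annotated, say that 319 evaluable, and so 400 enrolled per arm at 20% drop-out, corresponds to about 75% power on its stated inputs.

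The cost is two or three sentences and one table entry. Enrolment, the 544 target and the analysis stay as they are. The only drawback is that the power stated at the outset becomes less favourable.
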